Patients will be randomly assigned to one of the two treatment arms. The randomization schema will be based on parameters input into RANLST, a randomization program developed at UTMD Anderson and supported by an NCI grant.

C.6. Clinical Trial Design and Treatment Plan:

This study will have (1) Phase I: an initial non dose escalating phase to evaluate dose limiting toxicity. A total 30 evaluable patients will be enrolled in this phase. After study completion of the 30 evaluable patients (2) Phase II a second phase- RCT double blind phase will be started and (3) Both phases will have an open labeled phase. Patients in both Phase I or II may continue the ginseng in the open labeled extension phase if there are no grade 2 or more toxicity as per CTRC criteria as determined by the PI. A

total of 158 eligible patients will be enrolled in both phases of the trial (30 evaluable in phase I + 128 in phase II). (See Study Design Fig. 6).

Evaluable patients will be defined as any patient enrolled on the study that has taken at least one dose of treatment (i.e., either ginseng or placebo), making them available for toxicity and response.

C.6.1. Double-Blind Phase Dosing Patients will be randomized to one of two experimental groups receiving the treatments detailed below.

- The placebo group (**Arm 1**), will receive oral placebo twice daily for 29 days.
- The Panax ginseng group (Arm 2) will receive ginseng capsules 400 mg twice daily for 29 days.

Unblinding Procedure:

- 1. The Statistician and the investigational pharmacist will have access to the codes/assignments.
- 2. The codes will be revealed only If there is a safety issue and the treating physician needs to be aware of the treatment assignment.
- 3. The PI should be contacted regarding and give approval for un-blinding
- 4. The Investigator/research team must inform the IND Office when un-blinding occurs.

C.6.2. Open-Label extension Phase

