This is a preliminary study to explore the efficacy of P. ginseng in reducing fatigue as measured by the Functional Assessment of Cancer Therapy- Fatigue (FACIT-F) subscale. Because this Panax ginseng has not been previously evaluated in cancer related fatigue, we will implement this study in two phases. In the first phase(initial non dose escalating phase), we will enroll up to 30 patients in the Arm 2 (treatment arm); patients will not be enrolled in the placebo arm. Recruitment will be halted until these original 30 patients can be evaluated for DLTs. In the second, main phase patients will be randomized to receive either Panax ginseng or placebo. As a

2009-0854 January 21, 2016 Page 23 of 33

primary analysis, we will assess the level of fatigue at baseline and after 29 days to determine group differences in fatigue changes over time using analysis of variance. This analysis will test for differences between groups, differences over time, and a group by time interaction. We will also perform a repeated measures analysis by group using all available time points (for the FACIT-F fatigue subscale at baseline, day 15 and day 29). This analysis will test for differences between groups, differences over time, a group by time interaction, and trends over time. For all analyses of continuous variables, if the data are not approximately normally distributed, we will either use a nonparametric equivalent of the statistical test or we will transform the variable to achieve approximate normality. The design of the study is intent to treat, i.e., it is our aim to analyze anyone who received at least a single dose for both toxicity and response. Response would be considered clinical beneficial if they improve 3.5 points on the FACIT- F fatigue subscale at day 29 or day 15 (if day 29 is unavailable). Patient who have not completed at least day 15 would be considered inevaluable for consideration of clinical benefit.

Pilot Analysis:

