During the second phase of the study, the DSMB will meet to assess toxicity in an unblinded fashion at defined intervals (annual review) and will terminate the study if the incidence of DLT on either arm is judged by the DSMB to be excessive.

Power Considerations: There are no randomized controlled trials on P.ginseng for the management of CRF. The only intervention with Level I evidence for effectiveness in CRF is exercise. Among the most important clinical trials conducted on the intervention are those of Segal etal [154-156]. They have determined the clinically important difference in fatigue as a result of intervention as compared to placebo. Since these two studies used FACIT-F (our primary outcome) we have used these studies for power/sample size calculation. We postulate that if P.ginseng is an effective intervention we will observe a difference in response at Day 29(primary end point) similar and higher to those observed in the Exercise studies. We plan to include 50 evaluable patients per group. If we assume that our dropout rate will be no higher than 20%, we will recruit 64 patients into each group, for a total of 128 patients. As we could find no other published studies about the use of Panax ginseng in cancer patients, we base our sample size estimate on previous research in resistance exercise training [154]. This study found that the difference between groups in changes in the FACIT F subscale at 24 weeks was 4.78, significant at p=0.002, and was powered to detect a difference of 3.5 points based on a similar study in exercise resistance [155] that found standard deviations in difference scores over 12 weeks of 5.8. Studies such as Cella et al, 2002[156], state that differences of 3-5 points or more on the FACIT-F subscale are clinically important differences. If we assume a standard deviation of 5.8 in difference scores, with 50 evaluable patients per group we will be able to detect differences as small as 3.3 or larger with a twosided significance level of 0.05 and 80% power. With standard deviations in difference scores as large as 8.8, we will still be able to detect differences of 5 points or greater.

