Evaluable patients will be defined as any patient enrolled on the study that has taken at least one dose of treatment (i.e., either ginseng or placebo), making them available for toxicity and response. Although we expect dropouts (20% of 128 patients) the primary analysis will not include dropouts, but a secondary analysis would carry forward the last known FACIT-F score for those patients who had received at least one dose.

Yearly interim analyses will be conducted by the biostatistician and the results will be presented to the MDACC DSMB office. Results will be presented overall and by arm retaining the blinding as to arm assignment unless requested to reveal arm assignment by the DSMB (usually only made if one or both of the arms show a significantly less than expected efficacy or toxicity). In that case the statistician will reveal the arm assignments to the DSMB. The PI and other collaborators (other than the statistical collaborator) will remain blinded as to the arm assignments of patients.

As a part of each interim analysis, we will determine if either arm has significantly more occurrences of greater than grade 2 adverse events (p<0.05) as compared to each other. If this is found it will be reported to the DSMB and the study may be terminated early.

A formal interim analysis will be conducted when a total of 50 evaluable patients (one-half of the total number of evaluable patients) have been evaluated for 29 days. This interim analysis will allow for the early termination of the study in light of evidence that patients in either arm improve significantly than the other arm (early stopping due to superiority) or that patients in the two arms have similar improvement (early stopping due to futility). In order to provide for an overall two-sided significance level of approximately 0.05 for the study, the interim analysis will have a Lan-DeMets monitoring boundary with an O'Brien-Fleming stopping rule for both tests (EaSt, version 5, Cytel Software Corporation). The decision boundaries for the interim test will be to accept the null hypothesis of no treatment difference (futility) if the test statistic |Z| < 0.348 (p > 0.73), reject the null hypothesis if |Z| > 2.96 (p < 0.003), or otherwise continue the trial. The final test cut-off will be to reject the null hypothesis if |Z| > 1.95 (p < 0.051).

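### The primary FACIT-F test may move to a rank test or an unnamed transformation under a trigger and route that are not fixed in advance

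*Combined protocol and SAP*

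**What the plan says.** The opening of C.9 sets the primary analysis as an analysis of variance on the FACIT-F fatigue subscale at baseline and Day 29, with terms for group, time and their interaction. It then gives one rule for all continuous variables, the primary one included. Where the data do not look roughly normal, "we will either use a nonparametric equivalent of the statistical test or we will transform the variable to achieve approximate normality".

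A concrete trigger, Shapiro-Wilk, appears only under Pilot Analysis, for within-patient tests in the single-arm first phase.

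Power Considerations sizes the randomized phase in points of mean change: "If we assume a standard deviation of 5.8 in difference scores", then "with 50 evaluable patients per group we will be able to detect differences as small as 3.3 or larger", at a "twosided significance level of 0.05 and 80% power". The same paragraph cites a source for the statement that "differences of 3-5 points or more on the FACIT-F subscale are clinically important differences". The interim and final boundaries are meant to give an "overall two-sided significance level of approximately 0.05 for the study".

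On access to treatment codes, the Unblinding Procedure in C.6.1 states: "The Statistician and the investigational pharmacist will have access to the codes/assignments". C.9 has the biostatistician run yearly interim analyses by arm and exempts the statistical collaborator from the blind.

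**The concern.** The rule leaves four things open for the primary test: what counts as non-normal, whether scores, changes or residuals are examined, which of the two routes is taken, and which transformation is used. Nothing requires these to be settled before outcomes are linked to arm. Two things are at stake.

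- **Error rate.** A formal alpha and stopping boundaries presuppose one test. Several candidate tests with no fixed order leave room for a choice influenced by the result.
- **Meaning.** A difference in mean change can be read against 3.3 points and the 3 to 5 point range. A rank statistic or a difference in logs cannot.

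**Working it through.** **1. The plan's sizing is for a mean difference.** Inputs from Power Considerations: 50 per group, SD of change 5.8, difference 3.3, two-sided 0.05.

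- Standard error = 5.8 × √(2/50) = 5.8 × 0.2 = 1.16.
- 3.3/1.16 = 2.845; 2.845 − 1.960 = 0.885; power = Φ(0.885) = 0.81 (0.804 by noncentral t).
- The second case ("With standard deviations in difference scores as large as 8.8, we will still be able to detect differences of 5 points or greater") gives 5/(8.8 × 0.2) = 2.841 and power 0.81.

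Both reproduce the stated 80%. They apply to a comparison of means in points, so a test of means on untransformed scores is what the trial was sized for.

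**2. Type I error under different uses of the rule.** Null simulation: 50 per arm, SD of change 5.8, scores rounded and kept within 0 to 52, 12,000 trials per shape, single look at 0.05, Monte Carlo standard error about 0.002. These inputs are assumptions: baseline mean 24 and SD 9, mean change 3, the three shapes (normal, gamma with shape 1.5, t with 3 df) and the log and square-root transformations.

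| Use of the rule | Normal | Skewed | Heavy-tailed |
|---|---|---|---|
| t-test on change, fixed | 0.052 | 0.049 | 0.048 |
| Wilcoxon on change, fixed | 0.050 | 0.051 | 0.050 |
| Shapiro-Wilk gate, then Wilcoxon | 0.052 | 0.051 | 0.052 |
| Smaller p of t and Wilcoxon | 0.060 | 0.068 | 0.067 |
| Gate, then smallest p of Wilcoxon, log, square root | 0.054 | 0.078 | 0.076 |
| Smallest p of all four | 0.083 | 0.085 | 0.084 |

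Separate runs with other shapes and seeds gave 0.050 to 0.057 for a followed gate and 0.055 to 0.070 for the smaller of t and Wilcoxon. A gate followed by the better of rank and one log transformation gave 0.047 (normal), 0.061 (skewed) and 0.059 (heavy-tailed). The excess comes from choosing on the p-value, not from gating on normality. The fixed t-test holds its level, so a switch is not needed for validity.

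**3. Power of one fixed test.** Simulated at a 3.3-point shift, SD 5.8, 50 per arm, t-test against Wilcoxon on change:

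- normal: 0.80 against 0.78
- gamma, shape 2: 0.80 against 0.91
- t with 5 df: 0.80 against 0.87

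An unadjusted mean test can therefore lose 7 to 11 points in the non-normal cases. A second simulation put the loss at about 2 to 6 points.

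Baseline adjustment recovers power. With equal variances at the two visits and correlation ρ between them (an assumption; the documents give no value):

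- variance of change = 2σ²(1 − ρ)
- ANCOVA residual variance = σ²(1 − ρ²)
- ratio = (1 + ρ)/2

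Applied to SD 5.8:

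- ρ = 0.3: residual SD = 5.8 × √0.65 = 4.68; 3.3/(4.68 × 0.2) = 3.53; power = Φ(3.53 − 1.96) = 0.94.
- ρ = 0.7: residual SD = 5.8 × √0.85 = 5.35; 3.3/(5.35 × 0.2) = 3.09; power = Φ(3.09 − 1.96) = 0.87.

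Simulation over ρ from 0.3 to 0.7, with normal and non-normal shapes, gave the baseline-adjusted test power of 0.86 to 0.94 against 0.79 to 0.87 for the gated rule, with type I error of 0.046 to 0.057.

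**The case against.** The plan makes the switch depend on non-normality, not on the p-value. Read in good faith it is a gate, and a followed gate keeps the level. This stands: the figures above 0.06 describe misuse that the text does not rule out, not the plan's expected behaviour. The study also calls itself preliminary, and a rank p-value would not prevent reporting the mean difference or the planned 3.5-point benefit proportions.

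A reader might infer several stronger points that the documents do not support.

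- **An unblinded statistician will pick the test.** The statistician has the codes and is outside the blind, but no passage says who makes the choice or when. It is an inference.
- **The group-by-time interaction has no rank counterpart.** The primary analysis has two time points, so the interaction is a two-sample comparison of changes, for which the Wilcoxon rank-sum test is standard.
- **Changing test between looks breaks the boundaries.** With the stated boundaries (2.96, 0.348, 1.95), a t-test at the interim and Wilcoxon at the end gave overall error of 0.050 to 0.052, against 0.049 to 0.052 with the t-test at both.
- **Fixing the mean test costs no power.** For an unadjusted test this is wrong, as step 3 shows.

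What remains is that trigger, route and timing are open for the primary test, and that two of the three possible results are not in points.

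**Conclusion.** The concern holds in this limited form and is minor. The plan does not fix which primary test will be reported or on what scale. If a normality gate is set and followed, error stays near 0.05. If the choice followed the p-value, it could reach about 0.06 to 0.08. That is a worst case, possible rather than expected, and it rests on the assumed shapes and transformations. The mismatch of scale does not depend on those assumptions: only a mean difference in untransformed scores can be set against the 3.3-point sizing and the 3 to 5 point range. The power advantage of the adjusted test rests on the assumed baseline correlation of 0.3 to 0.7 and shrinks as that correlation approaches 1.

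**What to change.** State in C.9 that the single primary test, at both the interim and the final look and whatever the distribution, is the between-arm difference in mean untransformed FACIT-F fatigue score at Day 29, adjusted for baseline by ANCOVA. Name the Wilcoxon rank-sum test on change from baseline as a sensitivity analysis. Remove the primary endpoint from the general normality rule, and settle this before anyone sees outcomes by arm.

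The cost is wording, with no added patients. Some power may still be lost: with marked skewness and a high baseline correlation, a rank test could do better (0.91 in the gamma shape 2 case, against 0.86 at the low end for the adjusted test).

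A single gated rule, fully specified in advance, would also hold the error rate. It would leave the scale of the primary result to the data and had lower power in nearly all scenarios simulated, so it is the second choice.

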Secondary Analyses: We will compare the physical activity levels of participants in the two groups as measured by the hand grip dynamometer. We will also test the quality of life variables with the HADS and FACT-G tests. As each of these variables is also continuous and measured at the same points in time, we will determine the relationship of each of these variables to fatigue and analyze the data using repeated measures analyses as described above, testing for differences between groups, over time, and a time by group interaction. If several variables appear to be significantly related to fatigue, we will also perform multivariate analyses to determine the best predictors of fatigue as measured by the FACIT-F subscale. We will also determine relationships between daily or weekly fatigue, symptom data, and daily measures of sleep duration and fragmentation by determining correlation coefficients within time periods. Exploratory analyses of all subscale scores will be performed after the primary endpoint has been analyzed.

Summary information on the global symptom evaluation by group will also be provided at each of the assessed time points. Differences in distributions between groups will be analyzed using a chi-square analysis.

On an exploratory basis, we will also investigate whether or not different results were found for patients with different types of cancer, primarily using descriptive statistics. We do not expect to find statistical significance due to the low numbers of patients in each cancer type, but if we do find trends that appear to be significant, we will use this information to inform a future study. Additionally as a part of exploratory analysis, we will use Pearson chi-squared tests to compare the proportion of patients experiencing clinical benefit between each arm.

Information about toxic effects and tolerability will be summarized at each dose level. Safety assessments including hematology and chemistry assessments and toxicity evaluations will be made throughout the study (see Table 3).

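### The exploratory clinical-benefit comparison leaves out dosed patients who do not reach Day 15, against the plan's own one-dose aim, and mixes Day 15 with Day 29 responses

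*Combined protocol and SAP*

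**What the plan says.** All references are to the combined protocol and SAP.

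- **Aim (C.9, Statistical Analysis).** The design is described as intent to treat, explained as: "it is our aim to analyze anyone who received at least a single dose for both toxicity and response".
- **Evaluable patients (C.6, repeated in C.9 under Power Considerations).** These are "any patient enrolled on the study that has taken at least one dose of treatment", and both places add that such patients count for response as well as toxicity.
- **Benefit rule (C.9, directly after the aim).** A patient has clinical benefit if the FACIT-F fatigue subscale score rises by 3.5 points "at day 29 or day 15 (if day 29 is unavailable").
- **Exclusion (C.9, the next sentence).** "Patient who have not completed at least day 15 would be considered inevaluable for consideration of clinical benefit".
- **Use (C.9, Secondary Analyses).** "as a part of exploratory analysis, we will use Pearson chi-squared tests to compare the proportion of patients experiencing clinical benefit between each arm". Estimating and comparing these proportions is listed in section A.2, among the exploratory objectives.
- **Dropouts (C.9, Power Considerations).** For the FACIT-F score, "the primary analysis will not include dropouts, but a secondary analysis would carry forward the last known FACIT-F score" for patients with at least one dose. Nothing comparable is stated for the benefit proportion.

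**The concern.** The one-dose aim and the Day 15 exclusion cannot both govern the response analysis. An analyst must choose between them, and the choice fixes the denominator of a reported result.

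If the exclusion is followed, the denominator depends on something that happens after randomisation, namely staying on study to Day 15. The plan allows for up to 20% dropout. Its dose-modification table also takes patients off study drug for listed toxicities, so losses related to treatment are possible. If such losses fall unevenly, the two proportions describe differently selected groups.

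Separately, the numerator pools responses at two times, although Power Considerations names Day 29 as the primary time point. A patient who had improved at Day 15 and then left counts the same as one still improved at Day 29.

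At stake is how an exploratory result is read. The stated purpose of the exploratory data is to design a larger trial, and a benefit proportion is an easy figure to carry forward.

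**Working it through.** **1. The plan's own figures.** The documents state no figure for the benefit comparison. The sample size concerns the continuous score, and it reproduces. With SD 5.8, difference 3.3, two-sided 0.05 and 80% power, n = 2 × (1.960 + 0.842)² × 5.8² / 3.3² = 48.5, so 49 per group (stated: 50). For dropout, 50 / 0.8 = 62.5, so 63 (stated: 64). Neither figure depends on the benefit rule.

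**2. What the rule computes in one arm.** Let N be the number dosed, E the losses before Day 15, R the Day 29 responders, and L the patients without Day 29 data who had improved at Day 15.

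- Rule as written: (R + L) / (N − E)
- All dosed, Day 29 only, missing counted as non-response: R / N

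The first is never below the second. To see the range, assume N = 64, 13 lost (20%) and 40% benefit among the 51 Day 29 completers, so R = 20.4:

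- All dosed: 20.4 / 64 = 31.9%
- Rule, all 13 lost before Day 15: 20.4 / 51 = 40.0%
- Rule, all 13 lost after Day 15: from 20.4 / 64 = 31.9% (none improved at Day 15) to 33.4 / 64 = 52.2% (all improved)

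**3. Between arms: a gap created.** Assume 64 dosed and 24 Day 29 responders in each arm. Before Day 15, 2 placebo and 8 ginseng patients leave. Six further ginseng patients have Day 15 data only, and 3 of them had improved.

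| | Placebo | Ginseng | Gap |
|---|---|---|---|
| Rule, early exclusion only | 24/62 = 38.7% | 24/56 = 42.9% | 4.1 points |
| Rule, with Day 15 substitution | 24/62 = 38.7% | 27/56 = 48.2% | 9.5 points |
| All dosed, Day 29 | 24/64 = 37.5% | 24/64 = 37.5% | 0 |

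The substitution adds 3/56 = 5.4 points. Total loss is 16/128 = 12.5%, within the planned 20%, but it is uneven: 14/64 = 21.9% against 2/64 = 3.1%. The Pearson chi-squared statistic for 27/56 against 24/62 is 1.08 (p = 0.30), so the distortion would be in the estimate and not in a significant test.

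**4. Between arms: a gap hidden.** Keep the same early losses and no later ones, but let response among the remaining patients be equal at 24/62 = 38.7%. The rule then shows no difference. The expected number of ginseng responders is 0.387 × 56 = 21.7, so all-dosed counting gives 24/64 = 37.5% for placebo against 21.7/64 = 33.9% for ginseng, a gap of 3.6 points.

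**5. Equal loss.** If the amount, timing and response pattern of loss are the same in both arms, both methods show no gap when the arms respond equally.

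**The case against.** The strongest reply is that little rests on this comparison. It is labelled exploratory in both A.2 and C.9, and the primary test, sample size and interim boundaries do not use it. That stands, and it limits the weight of the point.

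The plan also limits missing data: after Table 3 it provides for completing FACIT-F by telephone when a visit is missed. The repeated-measures analysis uses all available time points, and a secondary analysis carries the last score forward. These help, but telephone contact only reduces gaps, and the other two are specified for the continuous score. None settles the denominator of the proportion.

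Step 3 of the working fixes the Day 29 responders at 24 per arm, which supposes that no early leaver would have responded. Step 4 drops that supposition, and then the all-dosed count shows the gap. Counting missing as failure is itself a single imputation. This also stands, and is why both results should be reported.

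Several stronger readings are tempting, and the documents do not support them:

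- **The rule rewards early dropout.** A patient lost before Day 15 is removed, not credited, and a later loss without improvement at Day 15 counts against the arm. The rate is raised only relative to counting losses as non-response.
- **The Day 15 substitution breaches intent to treat.** It keeps dosed patients in. Only the exclusion sentence conflicts with the aim.
- **Anyone without a Day 15 form is dropped.** The wording concerns not having completed at least Day 15, so a patient with Day 29 data but no Day 15 form is naturally scored at Day 29.
- **The result is biased toward ginseng.** The documents give no dropout by arm, so no direction follows.

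**Conclusion.** The internal conflict holds. C.9 and C.6 commit to analysing response in everyone with one dose, C.9 then excludes some of those patients from clinical benefit, and no other section reconciles the two. Mixing time points is a lesser, separate weakness.

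The size cannot be fixed from the documents. Under the stated assumptions the rule produced a 9.5-point gap where all-dosed counting showed none, and no gap where all-dosed counting showed 3.6 points. Distortion between arms requires losses that differ by arm in amount, timing or reason. The point is worth correcting before analysis, but it concerns an exploratory result. A reader should not infer that the primary conclusion is compromised by it.

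**What to change.** For the exploratory responder comparison in C.9:

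1. Take all dosed randomised patients as the denominator, which matches the plan's own definition of evaluable.
2. Score benefit at Day 29 and count a missing Day 29 value as non-response.
3. Keep the present rule (Day 15 substituted, early losses excluded) as a named sensitivity analysis, and report both results.
4. Tabulate missing FACIT-F data by arm and visit, so that a reader can see whether loss was uneven.
5. Amend the inevaluable sentence so that it applies only to the sensitivity analysis.

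The cost is wording and one extra table. Reported benefit rates will fall, possibly by several points: in the step 3 example ginseng goes from 48.2% to 37.5%. Non-response counting is a conservative imputation and should be described as one.

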We will summarize patient characteristics of all patients enrolled in the pilot study. Means and standard deviation or medians and IQRs will be calculated. We will also perform exploratory analyses on the changes in FACIT-F subscale (primary outcome measure) from baseline to Day 29 and baseline to Day 57. Similar analysis will be conducted for the secondary outcomes (FACT-G, ESAS symptoms, HADS, SDMT, six- minute walk test, Borg Scale, GSE and Hand Grip Strength and Endurance Test). Based on whether the data is normally distributed (Shapiro-Wilk test) we will use paired t-tests or Wilcoxon Ranked Sum tests. We will also summarize fatigue scores, other secondary outcomes at each point in time and the frequency and type of side effects as determined by NCI CTCAE V4 criteria.

Safety Monitoring

Safety Monitoring

Because this Panax ginseng has not been previously evaluated in cancer related fatigue, we will implement this study in two phases and we will utilize early stopping rules for dose-limiting toxicities (DLTs) for 30 patients in the treatment arm (Arm 2, Panax ginseng 800mg/day) before the main phase of the study begins. A DLT is defined as any Grade 3 or 4 toxicity that is attributable to the treatment regimen.

In the first phase, we will enroll up to 30 evaluable patients in the Arm 2 (treatment arm); patients will not be enrolled in the placebo arm. Recruitment for the main study will be delayed until these original 30 patients are evaluated for DLTs. We will base early stopping rules on a method proposed by Thall et al., (160) and using the Multc99 software from the Department of Biostatistics.

To ensure that the true DLT rate is sufficiently low, we will terminate the study early if the probability that the estimated toxicity rate is greater than 10% (given the results) is greater than 0.95. We assume a prior of Beta (0.1,0.9) in these calculations. The study will be stopped early if (# patients with DLT) / (# patients evaluated) >= 3/6, 4/10, 5/16, 6/22, or 7/29.

The table below shows operating characteristics given differing true toxicity rates based on 10000 simulations for each row:

	Probability	Achieved Sample Size		
True DLT rate	Early Stopping	25 th , 50 th , 75 th percentiles		
1%	<0.0001	30	30	30

Operating Characteristics for first phase early stopping rule (based on DLT)

3%	0.002	30	30	30
5%	0.013	30	30	30
8%	0.053	30	30	30
10%	0.116	30	30	30
15%	0.324	20	30	30
20%	0.597	9	21	30
25%	0.791	8	14	27
30%	0.917	6	9	17
40%	0.993	6	7	9

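### The one-arm pilot names a two-sample Wilcoxon test for within-patient changes and lists GSE as a change-from-baseline outcome although it has no baseline; the between-arm GSE test ignores response order

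*Combined protocol and SAP*

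**What the plan says.** **Pilot.** Phase I gives ginseng to up to 30 evaluable patients, and "patients will not be enrolled in the placebo arm" (C.9, Safety Monitoring). The Pilot Analysis paragraph plans "exploratory analyses on the changes in FACIT-F subscale (primary outcome measure) from baseline to Day 29 and baseline to Day 57". It then says "Similar analysis will be conducted for the secondary outcomes", and GSE is in the list that follows. A Shapiro-Wilk test decides between two methods: "we will use paired t-tests or Wilcoxon Ranked Sum tests". The opening of C.9 has a general rule for continuous variables that are not approximately normal: transform them, or use a "nonparametric equivalent of the statistical test".

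**GSE.** Section C.7.2.1 describes GSE as a rating of change since starting the medication: worse, about the same, or better, followed by a graded question. That section and Table 3 schedule it on Days 29 and 57 only.

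**GSE between arms.** Secondary Analyses says "Summary information on the global symptom evaluation by group will also be provided at each of the assessed time points", followed by "Differences in distributions between groups will be analyzed using a chi-square analysis". A later paragraph is more specific about a different endpoint: "we will use Pearson chi-squared tests to compare the proportion of patients experiencing clinical benefit between each arm".

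**Treatment after Day 29.** Placebo runs for 29 days (C.6.1). After the Day 29 assessment, patients of either arm who tolerated treatment may continue on open-label ginseng until Day 57 (C.6.2).

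**The concern.** The pilot has one arm and its target is the change within each patient, which is a single sample of differences. A rank-sum test can be applied only by treating the baseline and follow-up scores as two unrelated groups. That discards the pairing and can miss a real change. It also conflicts with the general rule in C.9, because the nonparametric equivalent of a paired t-test is the signed-rank test, which the protocol never names. The sentence covers FACIT-F and the whole list of secondary outcomes.

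GSE does not belong in that list. It is itself a change rating and has no baseline, so there is no change score to test.

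For the comparison of arms, a chi-square that ignores the order of the three answers gives up some sensitivity to a general shift towards better. The sentence also does not exclude Day 57, when placebo has ended.

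The stake is missed signals in exploratory and secondary results. GSE is named in A.2, and D.10 says trends in the secondary objectives will guide larger trials.

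**Working it through.** **1. The plan's own figure.** Power Considerations gives SD of change 5.8, 50 per group, difference 3.3, two-sided 0.05 and 80% power. Check: 3.3/5.8 = 0.569; 0.569 × √(50/2) = 2.84; 2.84 − 1.96 = 0.88, so power is about 81% (80.4% by the t-test). The figure reproduces. Nothing below challenges it; it supplies the SD of 5.8 and the reference shift of 0.57 SD.

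**2. What losing the pairing does.** Inputs: n = 30, SD of change 5.8, and a change of 3.5, which is the clinical-benefit threshold in C.9. The protocol gives no baseline-to-follow-up correlation r, so 0.3 to 0.85 is assumed.

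- SD of each score = 5.8/√(2(1 − r)).
- An unpaired comparison has expected statistic 3.5/SD × √(30/2), with true standard deviation √(1 − r) rather than 1.
- Approximate power is therefore P(N(mean, √(1 − r)) > 1.96).

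| r | SD of each score | Mean of statistic | Approximate power | Simulated rank-sum | Simulated signed-rank |
|---|---|---|---|---|---|
| 0.3 | 4.90 | 2.77 | 83% | 77% | 86-88% |
| 0.5 | 5.80 | 2.34 | 70% | 66% | 86-88% |
| 0.7 | 7.49 | 1.81 | 39% | 39% | 86-88% |
| 0.85 | 10.59 | 1.28 | 4% | 6% | 86-88% |

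Simulated type I error of the rank-sum test is at most 2.3%, so the error is conservative. These rows apply the rank test to every data set, which the plan does not do.

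**3. With the plan's gate.** The rank test is used only when Shapiro-Wilk rejects. So: loss = share of runs rejected × (signed-rank power − rank-sum power in those runs).

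- Normal changes: about 5% of runs reject. At r = 0.3, 0.05 × (87 − 77) = 0.5 points. At r = 0.85, 0.05 × (87 − 6) = 4 points. Direct simulation gives about 0 to 3 points in one run and at most about 4 in another.
- t (3 df) changes: 46-50% reject. 0.48 × (97.5 − 85) = 6 points; 0.48 × (97.5 − 8) = 43 points. Direct simulation: about 6 to 42.
- Gamma (shape 2) changes: 74-77% reject. 0.755 × (87.5 − 74) = 10 points; 0.755 × (87.5 − 5) = 62 points. Direct simulation: about 6 to 59.

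The ends of these ranges move by a few points between simulation runs. The pattern does not.

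**4. GSE in the pilot.** No arithmetic is needed. The Pilot Analysis calls for the same analysis of change from baseline; Table 3 has no baseline GSE.

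**5. GSE between arms, three answers.** Assumed: 50 per arm, a latent shift of 0.57 SD, and control splits worse/same/better of 30/25/45, 20/40/40, 20/50/30 and 15/25/60. The shift is borrowed from the FACIT-F sizing and is not a GSE design value. Power is 48-60% for the unordered Pearson test, 60-70% for chi-square for trend and 59-71% for a rank test. The gain from ordering is about 9 to 11 points. At an assumed shift of 0.4 SD the figures are 28-34%, 34-43% and 34-42%. Type I error at no shift is 4.2-5.4% for Pearson and 4.0-5.8% for trend, so both tests are valid.

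**The case against.** The strongest reply is that the pilot sentence cannot be followed literally. It analyses changes, which in one arm form a single sample, and a rank-sum test cannot be run on one sample. The general rule in C.9 then leads an analyst to the signed-rank test. Phase I exists to assess dose-limiting toxicity and has no efficacy power target, and the Shapiro-Wilk gate keeps the loss small when changes are near normal. On GSE, the plan asks about differences in distributions, which an ordinary chi-square answers. The restatement of aim A.2 in C.7.2.1 leaves GSE out.

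Most of this stands, and it limits the point to a wording correction with exploratory reach. It does not remove it: the specific sentence names the wrong test and would normally override the general rule, and none of this gives GSE a baseline.

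A reader might infer four stronger things that the documents do not support.

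- *The pilot loses most of its power.* That needs the literal reading together with clearly non-normal changes and a high correlation, all assumed.
- *The GSE chi-square is invalid or hopelessly sparse.* That would require an unordered test on the full graded responses. No passage says those will be tabulated.
- *The GSE timing is missing.* The assessment days are given.
- *The plan tests the arms at Day 57.* Reading the summary and chi-square sentences together allows this, but the test sentence names no day.

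**Conclusion.** The concern holds in a limited form, for exploratory and secondary analyses only.

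- **Wrong as written:** the two-sample test for paired changes, probably a slip for signed-rank, and GSE among the change-from-baseline outcomes. Under the plan's gate the power cost of the literal test is at most about 3 to 4 points for normal changes, about 6 to 42 for t (3 df) and about 6 to 59 for gamma (shape 2). These rest on n = 30, change 3.5, SD 5.8 and assumed correlations of 0.3 to 0.85. The direction, missed rather than false signals, does not depend on the assumed shapes.
- **Valid but improvable:** the GSE chi-square. Using the order of the three answers gains about 9 to 11 points at an assumed 0.57 SD shift, and less at smaller shifts.
- **Worth one sentence:** the status of Day-57 GSE. By then placebo has ended and patients of either arm may be on open-label ginseng, so a test by original arm would no longer compare ginseng with placebo.

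**What to change.** **Pilot Analysis.** Replace the rank-sum wording with the Wilcoxon signed-rank test, reported with the Hodges-Lehmann estimate and its confidence interval. Add a sign test if the changes are clearly skewed, because the signed-rank test assumes symmetry and under skew tests neither the mean nor the median. With gamma (shape 2) changes and n = 30 it rejected in 10-11% of runs when the true mean change was 0, and in about 9% when the true median was 0. Reporting the median alone does not cure this. Take GSE out of the change-from-baseline list and summarise it at Days 29 and 57.

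**Secondary Analyses.** Compare the arms on the three GSE answers at Day 29 with a chi-square for trend or a rank-sum test, which is appropriate there because the arms are independent. State that Day-57 GSE is descriptive by original arm.

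**Cost.** Wording only; no new data, visits or patients. The ordered test is less sensitive to a difference in spread alone, and the sign test usually has less power than the signed-rank test when changes are symmetric.
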